#### 7.1.3. Approved Methods of Contraception

A woman is considered to be of childbearing potential following menarche and until becoming postmenopausal, unless permanently sterile. Permanent sterilization methods include hysterectomy, bilateral salpingectomy, and bilateral oophorectomy. A postmenopausal state is defined as no menses for 12 months without an alternative medical cause.

Approved methods of contraception include:

 Combined (estrogen and progestogen containing) hormonal contraception associated with inhibition of ovulation:

- oral, intravaginal, or transdermal
- · Progestogen-only hormonal contraception associated with inhibition of ovulation:
  - oral, injectable, or implantable
- Intrauterine device
- Intrauterine hormone-releasing system
- Bilateral tubal occlusion
- Vasectomized partner (provided that the partner is the sole sexual partner of the WOCBP trial participant and that the vasectomized partner has received medical assessment of the surgical success)
- Sexual abstinence (defined as refraining from heterosexual intercourse during the entire period of risk associated with study treatments)
- Male condom with or without spermicide (for male study subjects with female partners of childbearing potential only)

Note: Sexual abstinence is only accepted when it is the preferred and usual lifestyle of the subject. Subjects must agree to use an approved method of contraception during the study and for 12 weeks after their last dose of study drug.

#### 7.2. Discontinuations and Subjects Lost to Follow-up

#### 7.2.1. Early Treatment Discontinuation and Study Withdrawal

A subject may withdraw from the study at any time, for any reason, without prejudice to his/her future medical care by the physician or at the institution. The investigator or sponsor may withdraw the subject at any time (eg, in the interest of the subject's safety). If a subject discontinues or is withdrawn from study treatment for any reason, the study site must immediately notify the medical monitor.

Once a subject is withdrawn from the study, the subject may not reenter the study.

Subjects who discontinue study treatment prior to the end of the main period should undergo all follow-up visits and procedures through the exit visit unless they are unwilling or unable or consent has been withdrawn. Subjects who wish to fully withdraw from the study before completion should be encouraged to complete the early termination visit as described in Section 9.5.

#### 7.2.2. Reasons for Discontinuation

The date of and reason for treatment discontinuation must be determined by the investigator and recorded in the subject's medical record. If it is determined that there was more than one reason for the discontinuation, each reason should be documented in the source document, and the most clinically relevant reason, as determined by the investigator, should be identified. Treatment may be discontinued and/or a subject's participation in the study may be discontinued for any of the following reasons:

- Any serious adverse event (SAE), clinically significant AE, severe laboratory
  abnormality, intercurrent illness, other medical condition (including infections),
  or circumstance that indicates to the investigator that continued participation is not in
  the best interest of the subject
- Subject withdrawal of consent: At any time, a subject's participation in the study may
  be terminated at his/her request or on the basis of the investigator's clinical judgment.
  The reason for subject withdrawal will be noted in the subject's source document.
- Subject fails to adhere to the protocol requirements (eg, drug noncompliance, failure to return for defined number of visits)
- Subject is lost to follow-up: the subject stopped coming for visits, and study
  personnel were unable to contact the subject
- Termination of the study by the sponsor or regulatory authorities
- Liver toxicity (refer to Section 7.2.3 for further details)
- Pregnancy, as indicated in Section 11.3
- Failure to meet randomization criteria

Any subject who discontinues treatment early or is withdrawn from the study early due to a treatment-emergent adverse event (TEAE), whether serious or nonserious, will be followed until the TEAE resolves (returns to normal or baseline values) or stabilizes or until it is judged by the investigator to no longer be clinically significant.

If consent is withdrawn, no further study evaluations are to be performed and no attempts are to be made to collect additional data.

Additionally, the sponsor may stop the study at any time for safety, regulatory, legal, or other reasons aligned with good clinical practice (GCP). This study may be terminated at the discretion of the sponsor or any regulatory agency. An investigator may elect to discontinue or stop the study at his/her study site for any reason, including safety or low enrollment.

#### 7.2.3. Liver Toxicity

Drug treatment continuation will be evaluated in case of any signs of possible drug-induced hepatic injury as follows:

Drug treatment will be discontinued immediately if either:

 alanine aminotransferase (ALT) or aspartate aminotransferase (AST) is >3× the ULN and (total bilirubin is >2× the ULN or international normalized ratio is >1.5)

or

ALT or AST is >8× the ULN

Drug treatment will be withheld if either:

ALT or AST is >5× the ULN

or

ALT or AST is >3× the ULN with the appearance of fatigue, nausea, vomiting, right upper quadrant pain or tenderness, fever, rash, and/or eosinophilia (>5%)

Drug treatment will be permanently discontinued and the subject withdrawn from the study if the condition persists for more than 2 weeks.

If the subject is not withdrawn from the study, drug treatment may be resumed when both ALT and AST are less than 1.5× ULN.

Any possible hepatic abnormalities will be monitored with repeat testing at a frequency of at least every 72 hours. Frequency of retesting will decrease to weekly or less once abnormalities stabilize. Repeat testing will discontinue once abnormalities are no longer detected.

Causes for the significant liver test abnormalities will be investigated (eg, acute viral hepatitis, Epstein-Barr virus, cytomegalovirus, herpes simplex virus, toxoplasmosis, varicella, and parvovirus), and subjects will be followed up until all abnormalities return to normal or to the baseline state.

Workup will also include consideration of alcoholic and autoimmune hepatitis, hepatobiliary disorders (eg, gallstones), nonalcoholic steatohepatitis, cardiovascular causes (eg, right-sided heart failure), and concomitant medications or supplements.

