#### 6.2.4. Follow-up Period

After completion of the main period, if a subject does not enter Part B, the long-term extension, they will need to complete the 8-week follow-up period.

Additionally, for those subjects who discontinue the main period but are willing to remain in the study, they should continue in the study by beginning the follow-up period. Depending on the timing of pegcetacoplan discontinuation, some assessments planned for Visits 15 and 16 may also be necessary.

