# 9.3. Follow-up Period

All subjects who complete study treatment and do not enter Part B, the long-term extension, will return to the investigator site for follow-up visits for 8 weeks, where assessments will be performed as per the Schedule of Activities (Table 1), and where the visit window allowances are also provided.

Subjects who discontinue treatment early and do not elect to continue their participation in the study will complete a follow-up visit 2 weeks after discontinuation of treatment and also the exit visit, 6 weeks thereafter.

The following assessments will be performed during this period, as outlined in the Schedule of Activities (Table 1):

- Procure 3 previously collected consecutive uPCR samples
  - Arrange courier pickup for all every 2-week triplicate uPCR samples during weeks without clinic visits
- Physical examination, brief
- Concomitant medications review
- Infusion site/pump safety assessment
- Blood samples for laboratory assessments
- Anti-pegcetacoplan peptide/anti-PEG circulating antibodies collection
- eGFR assessment
- Urinalysis collection

- Urine pregnancy test
- AE review
- Vital signs
- 12-lead ECG
- PK sample collection
- Dispense uPCR containers for consecutive collection every 2 weeks, per the following container dispersal schedule:
  - Dispense 3 containers (visits spaced every 2 weeks): Weeks 54, 56
  - Dispense 9 containers (visits spaced every 6 weeks): Weeks 58, 64, 70
- Dispense 24-hour urine collection container

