## 9.4. Exit Visit

All subjects will return to the clinic facility for the exit visit, 8 weeks following the final dose of pegcetacoplan, on Day 420 (or sooner if the subject discontinues prior to Week 52).

Study participation for each subject will be concluded following completion of the exit visit. If a subject withdraws from the study prior to the scheduled exit visit, all exit visit assessments should be performed at the subject's final visit to the clinic, including collection of blood samples for PK and/or PD assessments, as well as a postdose antigenicity sample, if not yet collected.

The exit visit procedures are listed in the Schedule of Activities (Table 1):

- Arrange courier service to pick up 24-hour urine collection to deliver to site
- Procure 3 previously collected consecutive uPCR samples to site
- Blood samples for laboratory assessments (see Schedule of Activities [Table 1] for details)
- Concomitant medications
- AE review
- Anti-pegcetacoplan/anti-PEG circulating antibodies assay
- eGFR assessment
- Urinalysis (see Schedule of Activities [Table 1] for details)
- Vital signs
- 12-lead ECG
- PK sample

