# 9.5. Early Termination and Exit Visit

Subjects who discontinue treatment early and do not elect to continue their participation in the study will complete an early termination visit. If the early termination visit is prior to Week 48, then all

assessments from Week 48, in addition to a renal biopsy, should be done, if possible. An additional exit visit should occur 6 weeks after the early termination visit. If the early termination is during the follow-up period, then all the assessments from the exit visit should be performed.

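### Protocol 7.2.3 mandates study withdrawal, not only a permanent drug stop, when a dose-hold liver abnormality lasts over 2 weeks, and the text on what follow-up then applies is in conflict

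*Protocol*

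**What the plan says.** **The liver rule.** Protocol 7.2.3 lists thresholds for stopping drug at once, then lower thresholds for withholding it. It continues: "Drug treatment will be permanently discontinued and the subject withdrawn from the study if the condition persists for more than 2 weeks". The next sentence confirms that leaving the study is meant, not only leaving the drug: "If the subject is not withdrawn from the study, drug treatment may be resumed when both ALT and AST are less than 1.5× ULN".

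**The default for stopping drug.** Under Protocol 7.2.1, subjects who stop treatment before the main period is over "should undergo all follow-up visits and procedures through the exit visit unless they are unwilling or unable or consent has been withdrawn". Section 6.2.4 agrees: "for those subjects who discontinue the main period but are willing to remain in the study, they should continue in the study". Section 9.4 opens with: "All subjects will return to the clinic facility for the exit visit, 8 weeks following the final dose of pegcetacoplan". Section 7.2.1 also says that a subject withdrawn from the study may not come back.

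**What is written for early leavers.**
- 9.3: subjects who stop early and choose not to continue "will complete a follow-up visit 2 weeks after discontinuation of treatment and also the exit visit, 6 weeks thereafter".
- 9.5: "Subjects who discontinue treatment early and do not elect to continue their participation in the study will complete an early termination visit", with a further exit visit 6 weeks later.
- 9.4, second paragraph: "If a subject withdraws from the study prior to the scheduled exit visit, all exit visit assessments should be performed at" the final clinic visit.
- 11.2: AE collection runs until the exit or early termination visit. SAEs suspected to be related stay reportable without time limit.
- 10.17 and Table 1 note O: anyone who stops dosing needs ADA samples 6 and 12 weeks after the last treatment.
- 7.2.2 and 7.2.3: the TEAE that led to withdrawal, and the liver abnormality itself, are followed to resolution, baseline or stability.

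**The concern.** Two decisions are tied together: ending the drug and ending participation. Elsewhere the protocol keeps them apart. A willing subject who stops drug for any other reason stays for off-drug visits, whereas this rule removes the choice and 7.2.1 closes the way back. The clause is not needed for safety, because 7.2.1 and 7.2.2 already let the investigator or sponsor withdraw a subject case by case.

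The protocol then does not settle what happens next. Sections 9.3 and 9.5 are worded for people who elect not to continue, and a subject removed by rule has elected nothing. The second paragraph of 9.4 can be met by a single final visit, and 11.2 can end AE collection there.

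At stake is off-drug safety information on a subject with possible drug-induced liver injury: new AEs other than SAEs suspected to be related, and the later PK samples. Safety over 52 weeks is a secondary objective, and SAP 7.1 counts TEAEs up to 56 days after the last dose.

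**Working it through.** **Inputs.** Week 52 is Day 364; the follow-up visits are Days 378, 392 and 420 (Protocol Table 1). Three PK and two ADA collections are planned in follow-up (Table 4). The TEAE window is 8 weeks in Protocol 12.4 and 56 days in SAP 7.1. Dosing is on Days 1 and 4 of each week (8.2), so the longest planned gap between doses is 4 days. The hold must last more than 14 days before withdrawal (7.2.3). The half-life is about 8 to 10 days (Amendment 3 rationale for the 8-week follow-up).

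**The plan's own figure.** 420 − 364 = 56 days = 8 weeks, so the exit visit closes the TEAE window exactly. The other two visits fall at 378 − 364 = 14 and 392 − 364 = 28 days.

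**Earliest withdrawal after the last dose.** Gap (0 to 4 days) + 14 days of hold = day 14 to day 18.

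**Consequence under each reading**, in days after the last dose:

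| Text applied | Visits | TEAE days not covered |
|---|---|---|
| 7.2.1 default | 14, 28, 56 | 0 |
| 9.4 opening sentence | exit at 56 | 0 |
| 9.3, counted from the last dose | 14 and 14 + 42 = 56 | 0 |
| 9.3, counted from a permanent stop on day 14 | 14 + 14 = 28 and 28 + 42 = 70 | 0 |
| 9.5, early termination visit at withdrawal | 14 to 18, exit at 56 to 60 | 0 |
| 9.4 second paragraph, final visit at withdrawal | 14 to 18 only | 56 − 14 = 42 to 56 − 18 = 38 |

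The last row is 42/56 = 75% to 38/56 = 68% of the window. It is an upper bound, because a later withdrawal leaves fewer days uncovered.

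**PK.** The default gives three follow-up samples. Under 9.3 counted from the last dose, the +28 sample drops out (2 of 3 kept). Under the last row, 1 of 3 is kept.

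**Drug still present**, assuming simple first-order decline, 2^(−t/half-life):
- Day 14: 29.7% (half-life 8 days) to 37.9% (10 days).
- Day 18: 21.0% to 28.7%.
- Day 56: 0.8% to 2.1%.

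In the worst reading, then, observation stops with about 21% to 38% of drug remaining, whereas the 8-week period was chosen to cover washout.

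**ADA.** The scheduled follow-up samples are at +14 and +56 days. Section 10.17 separately asks for samples at 6 × 7 = 42 and 12 × 7 = 84 days, triggered by stopping dosing and not by study status. Day 42 lies inside the 56-day window.

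**Weight of one subject.** 1/12 = 8.3% of the maximum sample. The documents give no frequency for this liver path.

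**The case against.** The best reply is that the gap appears only if similar wording is read in two ways. To lose 38 to 42 days, one must read 9.3 and 9.5 strictly (they cover only subjects who choose to leave) and the second paragraph of 9.4 broadly (a subject who withdraws includes one who is removed). Read strictly throughout, the opening sentence of 9.4 still brings every subject back at 8 weeks. Read broadly throughout, 9.3 and 9.5 supply the exit visit. Section 7.2.1 could also be applied directly, since this subject has stopped treatment and being removed by rule is not among its stated exceptions. This argument stands: the loss is possible, not established.

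It is also fair that the most relevant data are kept. Liver retesting, the causative TEAE and related SAEs are all followed, and 11.2 asks for appropriate follow-up of subjects whose AEs stop drug.

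The contrast with the more severe thresholds needs care. A reader might infer that milder cases are removed from the study while severe ones are not. The withdrawal sentence is a separate paragraph after both lists, and the condition it refers to is not named. Tying it to the hold branch is the natural reading, because the next sentence is about resuming drug, but the layout does not prove it.

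What the reply does not remove is the instruction itself. Section 7.2.3 orders withdrawal in plain terms, against the default, and a site must guess which later section applies.

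**Conclusion.** The point holds as a minor one. A mandatory study withdrawal contradicts the protocol's own follow-up default, and the text on what follows is in conflict. For an affected subject the uncovered part of the TEAE window ranges from 0 to about 38 to 42 of 56 days. The upper end assumes withdrawal as soon as the hold passes 14 days, a last dose 0 to 4 days before the hold, and a final visit that replaces the exit visit.

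Four stronger conclusions might be inferred; the documents do not support them.
- *That follow-up is lost.* Most readings cover the full 56 days.
- *That ADA data are lost.* Section 10.17 requires samples at 6 and 12 weeks whatever the study status, so this is a conflict of text.
- *That this clause distorts AE percentages.* SAP 13.1 divides by everyone in the analysis set, but that affects every early dropout alike.
- *That the primary result or the Week 12 biopsy is compromised by this sentence.* SAP 6.1 already counts stopping treatment as non-reduction in the composite analysis, and the default follow-up period schedules no biopsy either.

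No error rate or sample size is involved; the trial is descriptive and the path is probably rare.

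**What to change.** Change two adjacent sentences in Protocol 7.2.3, together.

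1. Replace the clause that withdraws the subject from the study with: *and the subject followed per Section 7.2.1 through the exit visit, with ADA samples per Section 10.17*.
2. Change the condition that opens the next sentence to: *If drug treatment has not been permanently discontinued*. Keep the 1.5× ULN threshold for resuming. Without this second edit, the existing condition (not withdrawn from the study) would allow a restart after a permanent stop.

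Leave study withdrawal as a case-by-case decision under 7.2.1 and 7.2.2.

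The cost is the wording of two sentences and, per affected subject, up to two off-drug visits that are already in the schedule. The subject may decline them under 7.2.1.

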#### 7.2.4. Subjects Lost to Follow-up Prior to Last Scheduled Visit

A minimum of 3 documented attempts must be made to contact any subjects lost to follow-up at any time point prior to the last scheduled contact (office visit or telephone contact). At least 1 of these documented attempts must include a written communication sent to the subject's last known address via courier or mail (with an acknowledgment of receipt request) asking that the subject return to the site for final safety evaluations and to return any investigational product.

#### 7.2.5. Replacement of Subjects

Subjects who discontinue treatment early or withdraw from the study early for reasons not related to the safety of pegcetacoplan may be replaced at the sponsor's discretion to ensure that the objectives of the study are met. Subjects assigned to treatment who discontinue or withdraw from the study may be replaced until 12 subjects complete Week 52 of the study.

#### 8. TREATMENTS

#### 8.1. Details of Study Treatments

The test product is pegcetacoplan, which will be provided as a sterile solution of pegcetacoplan 1080 mg/20 mL in acetate-buffered sorbitol, supplied in stoppered glass vials. Additional information is provided in the pegcetacoplan IB.

#### 8.2. Dosage Selection

The dose of pegcetacoplan is 1080 mg twice per week via SC infusion (20 mL) during the main period of Part A (with dosing not beginning for Group 2 until Week 13) and during Part B. As noted in Section 4.2.1, this study uses the same 1080 mg twice weekly dosing schedule currently used in the Phase 3 studies in patients with PNH. This dose was also evaluated in Study APL2-201, a Phase 2 study that enrolled patients with C3G.

Group 1 subjects will receive their initial doses of pegcetacoplan at the scheduled clinic visit on Day 1 and will continue to receive their pegcetacoplan (1080 mg/20 mL twice a week) on Day 1 and Day 4 of each treatment week until Week 52 if they do not enter Part B; however, if they do enter Part B, the treatment schedule will continue as during Part A.

Group 2 subjects will receive their initial doses of pegcetacoplan after the Week 12 renal biopsy (see Schedule of Activities [Table 1]) and will continue to receive pegcetacoplan (1080 mg/20 mL twice a week) on Day 1 and Day 4 of each treatment week until Week 52 if they do not enter Part B; however, if they do enter Part B, the treatment schedule will continue as during Part A.

Dosing diaries will be utilized for pegcetacoplan and are to be completed for each dose administered at the clinic or outside regular clinic visits. Subjects should ideally maintain a consistent dosing schedule and should not delay or defer dosing. Missed doses will be handled on a case-by-case basis between the investigator and medical monitor, with the general approach being to administer a missed dose as soon as noticed, unless the next dose has already been administered.

#### 8.3. Investigational Product Administration

Investigational product, pegcetacoplan, will be administered as a 20-mL SC infusion.

The preferred site of infusion will be the abdomen. If administration into the abdomen is not feasible, alternative appropriate sites are acceptable (see pharmacy manual for more details). Research nurses or other appropriately qualified research personnel will administer the SC infusions (as needed) and will qualify and supervise the self-administration (or caregiver administration). These qualified personnel will be made available for a minimum of 6 days on treatment (2 doses) to ensure the subject has been qualified to conduct self-administration; duration could be shortened if qualification happens sooner. During qualification, the subject (or caregiver) must demonstrate to the research personnel their ability to safely and effectively administer study drug using the infusion pump. Following self-administration qualification, subjects may self-administer the SC infusions without supervision. Once qualified, the subject will continue to self-administer infusions at the clinic on those days when a clinic visit occurs and at an off-site location convenient to the subject on all other days. Self-administration conducted at the clinic will be supervised to ensure that the subject continues to remain compliant with the administration guidelines.

NOTE: If the subject requires further training, the self-administration qualification period may be extended beyond 6 days on treatment (2 doses). Self-administration may also be conducted by a member of the subject's household or family member, etc, who will undergo the same qualification criteria by the in-home medical professional (qualification is not intended to be restricted to the subject). Please refer to the pharmacy manual for further details regarding self-administration qualification.

